Trial registry will be completed at www.clinicaltrials.gov. The randomised controlled trial (RCT) is registered under id no: NCT03798288. Registration was completed before recruitment of participants to the RCT was initiated.

Roles and responsibilities:

The partners involved in the selfBACK project include:

1. The Norwegian University of Science and Technology (NTNU), Trondheim, Norway
2. The University of Glasgow (GLA), Glasgow, Scotland
3. The Robert Gordon University (RGU), Aberdeen, Scotland
4. Trade eXpansion (TRX), Tommerup, Denmark
5. National Research Centre for the Working Environment (NFA), Copenhagen, Denmark
6. Health Leads BV (HLE), Amsterdam, Netherlands
7. University of Southern Denmark (UoSD), Odense, Denmark

NTNU is leading the development of the underlying structure for the database and decision support system (DSS), RGU has been leading the physical activity monitoring and TRX has been leading the mobile app development. The medical partners (NTNU, GLA, RGU, NFA and UoSD) have developed content for the app. The RCT is a multi-centre trial, patients are recruited at NTNU and UoSD; UoSD is lead in the planning and conducting of the RCT; UoSD is lead in the process evaluation. NTNU is leading the overall project.

Funding

The selfBACK project has received funding from the European Union Horizon 2020 research and innovation programme under grant agreement no 689043. The funding body supervises the conduct of the overall project, but is not involved in the planning, implementation and interpretation of data from the RCT.

1. Introduction

Low back pain (LBP) is worldwide a major contributor to years lived with pain and disability. In the Global Burden of Disease studies of 2010 and 2015, it was estimated that LBP is the leading cause of years lived with disability in most countries [4, 5]. In the vast majority of people experiencing LBP specific pathoanatomical causes cannot be identified and more than 85% of people seen in primary care are categorised as having "non-specific" LBP [6]. The economic costs of health-care, sickness absence, lost ability to work, social benefits and treatment costs of non-specific LBP are high and can be considered a societal burden [7-9].

Clinical guidelines recommend patient education, exercise therapy, multidisciplinary treatments and combined physical and psychological interventions to manage LBP [10-14]. Although national clinical guidelines may differ in scope and context, the recommendations are rather consistent across countries [10-12, 15-17]. Self-management programmes that include elements of such recommended treatment components have been suggested as a promising option for chronic conditions including non-specific LBP [18]. Self-management may be defined as the individual's ability to care for own health by managing symptoms, physical and psychological consequences and impact on life [18]. In LBP, the effectiveness of self-management has been reported to be moderate for pain and small to moderate for disability [19, 20]. The lack of effect is likely to be explained by lack of tailoring of the programme to the individual and support to persist with self-management [21], and such factors may also have a negative effect on adherence to self-management programmes. Lastly, as self-management is broadly defined, the content of self-management programmes varies between the reported trials [19].

Digital solutions, such as mobile applications (apps), have been suggested as platforms for supporting self-management of chronic conditions [22, 23]. Within recent years, a vast number of apps has been introduced to the commercial market for self-management of LBP. A 2016 systematic review identified 61 apps and concluded that available apps have poor quality, included poor quality information from questionable sources and that none of the apps had been tested for effectiveness [24]. While a recent systematic review by the SELFBACK team highlighted that the literature is heterogeneous, and the evidence base remains weak [25], the SELFBACK project aims to fill this knowledge gap by developing an evidence-based and data-driven decision support system (DSS) delivered via a smartphone app to facilitate, improve and reinforce self-management of non-specific LBP [26]. The DSS suggests self-management plans consisting of physical activity advice, patient education and recommendations for physical exercise tailored to the individual's specific health information. The effectiveness of the DSS will be evaluated in a RCT. Additionally, a process evaluation will be carried out in parallel to the RCT (section 8) [27], as this will be important to aid understanding of uptake and utilisation as well as future implementability.

1.1. Objectives

The objective is to evaluate the effectiveness of the SELFBACK DSS in addition to usual care versus usual care only in a RCT. Primary outcome is pain-related disability at three months (primary endpoint). We hypothesise that participants randomised to using the SELFBACK app in addition to usual care will have at least two points difference in pain-related disability at three months, measured by the Roland-Morris Disability Questionnaire (RMDQ), compared to participants receiving usual care only.

The effectiveness of the intervention on secondary outcomes, including quality of life, use of non-prescriptive medication, sleep problems, depressive symptoms, stress, functional ability and pain

intensity, will be assessed at three months. We will also evaluate the effect on these outcomes at six and nine months.

2. Methods

2.1. Trial design

The SELFBACK study is designed as an international multi-centre superiority RCT with two parallel groups, testing the relative effectiveness of the SELFBACK DSS in addition to usual care (intervention group) versus usual care only (control group) for participants with non-specific LBP.

2.2. Study setting

The recruitment of participants will be conducted in two countries: Trondheim, Norway (NO) and Odense, Denmark (DK). In both NO and DK, participants will be recruited from general practice, physiotherapy and chiropractic clinics. Additionally, in DK recruitment will also be from the Spine Centre in the Region of Southern Denmark. The Spine Centre is an outpatient hospital that reviews patients with back pain referred from primary care. The Spine Centre provides diagnostic assessment of patients and prescribes treatment plans according to national treatment guidelines. Patients seen at the Spine Centre without serious pathologies will be referred to the SELFBACK study.

2.3. Selection criteria

Participants must meet all the following eligibility criteria:

- Seeking care from primary health-care practice or a specialised outpatient hospital facility (DK) for non-specific LBP within the past 8 weeks
- LBP of any duration
- Mild-to severe pain-related disability rated as 6 or above on the Roland Morris Disability Questionnaire (RMDQ)
- Age ≥ 18 years
- Own and regularly use a smart phone (with at least Android 6.0+ or iOS11.0+) with internet access (Wi-Fi and/or mobile data)
- Have a working email address and have access to a computer with internet access to complete questionnaires in a web browser.

Presence of any of the following criteria will exclude participants from enrolling in the RCT:

- Not interested
- Unable to speak, read or write in the national language (Danish/ Norwegian)
- Cognitive impairment or learning disabilities
- Mental or physical disease or health problem limiting participation in the study (Examples are fractures or pathologies, such as cancer, inflammatory diseases, and signs of radiculopathy (severe leg pain, loss of leg strength, or loss of or altered sensation in a myotomal or dermatomal distribution))
- Unable to take part in exercise/physical activity (such as non-ambulatory patients, use of walking aids/assistance, unable to get down and up from the floor independently)
- Fibromyalgia (diagnosed by a health care professional (HCP))

- Pregnancy
- Previous back surgery
- Ongoing participation in other research trials for LBP management.

The assessment of whether the criteria are considered to limit participation is performed either by the referring HCP during the recruitment phase (see green box in **Figure 1**) or by participant self-report during the screening call (see blue box in **Figure 1**).

2.4. Identification and recruitment of participants by health care professionals (HCP)

The recruitment period is planned to start in March 2019. A total of 350 participants are to be recruited to the RCT. Of these, 75% (n=262) will be recruited in DK and 25% in NO (n=88). In each country, collaborations with local clinics and HCPs will be established to facilitate recruitment. The number of clinics and HCPs needed to ensure sufficient recruitment rate has been informed by the pilot study (August 2018–January 2019).

The recruitment process is outlined in the green box in **Figure 1**. Patients seeking care due to non-specific LBP will be invited to participate in the trial. The HCP will refer potentially eligible participants based on a short description of eligibility. Final eligibility will be assessed by the research team during a screening phone call (blue box in **Figure 1**). The referral to the selfBACK trial will take place after the HCP has performed routine diagnostic assessment or treatment (usual care). Participants are recruited through two pathways, *registry data or live recruitment*.

Recruitment from registries will be conducted at the Spine Centre in DK. Participants are sent an invitation letter including written information about the project. The written information describes three ways to contact the research team, if the participant is interested in the project: 1) by email, 2) telephone (call or text message), or 3) a link where contact information can be entered. For the registry recruitment in DK, a list of patients will be extracted every week from the Spine Centre's registry, who consulted in the past week with LBP according to the inclusion criteria.

For the live recruitment of participants, the HCP identifies patients seen in their clinical practice who are eligible for self-management of LBP. The HCP briefly informs the patient about the project and provides the patient with written information. This information is the same as given in the registry recruitment. If interested, patients can contact the research team by 1) email, 2) telephone (call or text message), or 3) add their contact information to a sign-up sheet at the clinic.

2.5. Screening for eligibility and enrolment by researchers

The screening process is outlined in the blue box in **Figure 1**. Participants who have indicated that they are interested in the project are contacted via telephone by a researcher in the selfBACK team. During this call, oral information about the trial is given to the participant and questions about the project and project participation can be answered. A detailed eligibility screening is performed via a pre-defined screening form including the inclusion and exclusion criteria described above.

The enrolment process is outlined in the grey box in **Figure 1**. If eligible and willing to participate, the participants give their verbal consent to participate and are sent an email with a link to the web-based baseline questionnaire. After a participant has completed the baseline questionnaire the informed consent will be signed, and the randomisation performed via a web-based randomisation system (see section 2.6). A small difference in this procedure is evident between countries due to

difference in requirements from the local Ethics Committees. In NO, the written consent form is included in the written information provided by the HCP. The participant can return the signed informed consent in a pre-stamped envelope as provided by the HCP or alternatively, the participant can take a picture of the signed consent form and send it via a text message to the researchers. Hereafter, the researcher will call the participant and inform about the result of the randomisation and give instructions according to group allocation. If randomised to the control group, all instructions are completed on the phone. If randomised to the intervention group, the participant is required to attend a face-to-face meeting to have the app installed on their phone and be given the wristband to wear. In DK, all participants are invited to a face-to-face meeting, where the consent form is signed and hereafter the randomisation is performed. All instructions are given verbally at this meeting.

If randomised to a) the selfBACK DSS in addition to usual care, participants are given wearable device along with instructions and assistance on how to download, install and pair the wearable device with the app and how to connect the apps on the smartphone (see section 3.2.1). Moreover, the participant is given information about their follow-up assessments and information on how to contact the researcher if needed. If a participant declines participation at the face-to-face meeting, the researcher will ensure that the information from the baseline questionnaire is deleted.

If randomised to b) usual care, participants are instructed on the principles of usual care, and are given the same information as the selfBACK intervention group about the follow-up assessments and how to get in touch with the researcher if needed.

The flow of participants through the trial is described in **Figure 1**.

[figure not shown]

Figure 1: Participant flow through selfBACK trial. Abbreviations: GP: general practitioner, PT: physiotherapist, C: chiropractor, HCP: Health care provider, LBP: Low Back Pain

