5.2. Statistical analysis

The primary analysis will estimate the mean difference with a 95% confidence interval (CI) in RMDQ score at three months follow-up between groups (selfBACK in addition to usual care versus usual care only). The analyses will be conducted according to the intention-to-treat principle using a linear mixed model for repeated measures. This model includes all available data for all participants at each time point (i.e. baseline, six weeks, and three months). In the regression model, individual participants will be specified as a random effect, accounting for the within subject covariance structure. The effect of group and time will be specified as fixed effects using a joint variable of intervention and time. Here, baseline levels are pooled over the two study groups assuming that any baseline differences are due to chance [73]; this also controls for any baseline differences in the outcome variable. The analysis will investigate the effect of the intervention as constant over time, as well as an interaction between time and group allocation. The between group difference will be estimated both in a crude model, and adjusted for the two variables used for stratification in the randomisation i.e. country and care provider [74]. Further adjustment for baseline levels of other prognostic factors will be considered.

Any missing values are inherently accounted for in the mixed model approach [75], but multiple imputation methods and complete case analysis will be applied in sensitivity analyses. Possible modifiers of the effect of intervention on the primary outcome will be assessed in supplementary analyses stratified by gender, age groups, socioeconomic status and different levels of LBP severity etc., and accompanied by tests of statistical interaction.

Secondary outcomes will be analysed using a similar approach as described above for the primary outcome, with linear mixed models for repeated measures. Analyses of data from six- and nine-months follow-up will also be analysed according to the above description for the primary outcome. The precision of the estimates from the statistical analyses will be assessed by 95% CI.

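### The rule to delete baseline data at the face-to-face meeting is not limited to people not yet randomised, and in Norway it can reach only the app arm

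*Protocol*

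**What the plan says.** Protocol section 2.5 gives a general order of steps: "After a participant has completed the baseline questionnaire the informed consent will be signed, and the randomisation performed via a web-based randomisation system". The baseline questionnaire is answered on verbal consent. The countries then differ.

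- **Norway.** Signed consent comes back by post or as a photograph, and randomisation follows. Then: "Hereafter, the researcher will call the participant and inform about the result of the randomisation and give instructions according to group allocation". For controls: "If randomised to the control group, all instructions are completed on the phone". For the app arm: "If randomised to the intervention group, the participant is required to attend a face-to-face meeting to have the app installed on their phone".
- **Denmark.** "In DK, all participants are invited to a face-to-face meeting, where the consent form is signed and hereafter the randomisation is performed". Instructions are given at the same meeting.

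The deletion rule stands in the paragraph of section 2.5 on people allocated to the app: "If a participant declines participation at the face-to-face meeting, the researcher will ensure that the information from the baseline questionnaire is deleted". The paragraph on usual care has no counterpart.

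Section 5.2 sets the analysis: "The analyses will be conducted according to the intention-to-treat principle using a linear mixed model for repeated measures". It adds: "This model includes all available data for all participants at each time point", and baseline is one of those time points. No exception is made for people who decline after randomisation.

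**The concern.** Intention-to-treat requires that everyone randomised stays in the arm allocated and that nothing done after allocation decides who is counted. A deletion rule is harmless while it applies only before randomisation. Once it can act afterwards, and can act in one arm but not the other, the groups compared may no longer be those that were randomised.

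The loss is also hard to repair. The randomisation system keeps a minimal record (section 2.6: id, country, care provider, site, age, gender), so decliners can still be counted. It holds no RMDQ score, so nobody could later show how disabled the decliners were at entry, and the multiple imputation planned as a sensitivity analysis would have no baseline score for them.

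**Working it through.** **1. Who can be reached by the rule**

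| | Consent and randomisation | Who attends a meeting | What a decline at the meeting means |
|---|---|---|---|
| Norway, app | before the meeting | all (required) | always after randomisation |
| Norway, control | before the telephone call | nobody | cannot occur |
| Denmark, both arms | at the meeting | all | before consent, or after allocation |

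The Norwegian result does not depend on where the sentence is placed. If the rule belongs only to the app paragraph, it acts after randomisation in the app arm. If it applies to any face-to-face meeting, the only such meeting described for Norway is still that of the app arm.

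**2. How many people are exposed**

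- Plan (protocol section 2.4): 0.25 × 350 = 87.5, stated as 88; with Denmark's 262 this makes 350, so the split reproduces. At 1:1, 88/2 = 44 Norwegian app participants, and 44/175 = 25% of the arm.
- Enrolment reached (SAP, Settings and Participants): 461, of whom 144 in Norway. 144/2 = 72, and 72/(461/2) = 72/230.5 = 31% of the arm. Arm sizes by country are not given; 1:1 is assumed.
- Norwegian controls exposed: 0 in both cases.

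**3. Possible shift in the three-month difference**

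Let f be the share of Norwegian app participants who decline at the meeting and give no follow-up. Let d be the RMDQ gap between them and those who stay. Neither is in the documents; both are assumptions.

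Crude shift = d × (f × number exposed) / arm size. With d = 4:

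| f | Planned: people lost | Planned: shift | Reached: people lost | Reached: shift |
|---|---|---|---|---|
| 2% | 0.9 | 0.02 | 1.4 | 0.02 |
| 5% | 2.2 | 0.05 | 3.6 | 0.06 |
| 10% | 4.4 | 0.10 | 7.2 | 0.12 |
| 20% | 8.8 | 0.20 | 14.4 | 0.25 |

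Example: 4 × (0.05 × 44)/175 = 0.05. The shift is proportional to d. Against the two-point target, the planned column is 1% to 10%.

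**4. How much of that is due to the deletion itself**

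With a pooled baseline mean m, correlation ρ = 0.4 (section 5.1) and equal SDs, the model estimates each arm's follow-up mean as (mean follow-up score) + ρ × (m − mean baseline score), both means taken over people with follow-up. In the difference between arms m cancels:

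Difference = (F_app − F_control) − 0.4 × (B_app − B_control), where F and B are those follow-up and baseline means.

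Someone with a baseline score and no follow-up enters only through m. With the correlation and SD held at the design values, keeping or deleting that score leaves the primary difference unchanged. If the gap d already exists at baseline, the B term removes 40% of the crude shift either way, leaving for example 0.6 × 0.20 = 0.12. If it does not, nothing is removed. The shift in step 3 is thus the price of missing follow-up.

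**The case against.** The best defence is that the sentence is consent housekeeping. The baseline questionnaire is completed on verbal consent. A Dane who comes to the meeting and refuses to sign leaves data without written consent, and those data should be deleted. A Norwegian app participant has already signed and been told the allocation, so withdrawing would be the more natural word for leaving at that stage. If declining means withdrawing consent to use of data, deletion may even be required. This is plausible and rules out any firm claim about intent. It does not clear the text, which sets no such limit although the same section spells out the differences between the countries.

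Some further points stand. Norwegians who refuse on the telephone never reach the meeting, so the rule does not cover them. It deletes only the baseline questionnaire; it does not stop follow-up, and the model can use follow-up scores without a baseline. Figure 1 is not shown and the main trial's own analysis plan was not supplied; either might settle the matter. The supplied SAP uses Danish participants only, so the Norwegian asymmetry does not reach it.

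A reader might go further and infer that Norwegian records were in fact erased, or that the rule biases the primary result by some tenths of a point in favour of the app. The documents support neither. They report no such deletion, give neither a decline rate nor a direction for the gap, and step 4 shows that the arithmetic concerns lost outcomes. Nor do they support the opposite inference that Denmark is safe because its meeting precedes randomisation: allocation happens during that meeting. SAP Table 3 shows no missing baseline RMDQ among the 300 Danes analysed there, but it is silent on the other 17 of 317 and on anyone not counted.

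**Conclusion.** The point holds as a defect in the rule as written. It permits removal of baseline data after randomisation, in Norway from the app arm alone, and this cannot be reconciled with the analysis promised in section 5.2. That conclusion needs no assumption beyond the order of steps in section 2.5.

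The numerical consequence is probably small. If 2% to 20% of Norwegian app participants declined and differed by 4 points, the crude shift would be about 0.02 to 0.25 RMDQ points, mostly or wholly from missing follow-up. It would favour the app only if decliners would have done worse. Whether anyone was affected cannot be told from the documents. It should be corrected because the remedy is cheap, not because the primary result is shown to be in doubt.

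**What to change.** Replace the sentence in section 2.5 with one that does three things:

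1. Limits deletion of the baseline questionnaire to people who decline before they are randomised, in either country.
2. States that everyone randomised keeps the baseline record, is invited to all follow-ups and is analysed in the arm allocated, unless they withdraw consent to use of their data. Declining the app, leaving the trial and withdrawing data should be named as separate events.
3. Requires post-randomisation decliners, and any records deleted, to be reported by arm and country.

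Continued follow-up protects the estimate; the kept baseline allows decliners to be described and used in sensitivity analyses. The SAP says that the trial is complete, so what can still be done is the third item: state whether any randomised participant's record was deleted. The cost is one protocol sentence and a line in the participant flow. The small downside is that a few participants with baseline data only remain in the analysis set.
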